6.0 Study Procedures

General Approach: This is a prospective cross-over trial that will enroll eligible patients with CPVT and perform a baseline treadmill exercise tolerance test (ETT) followed by a repeat treadmill ETT with I.V. atropine administered immediately prior to exercise. Atropine is a parasympathetic blocker and results in sinus tachycardia, which is expected to reduce the diastolic interval thereby reducing delayed after depolarizations and ventricular ectopy compared to baseline. Both ETTs will be performed on the same day with two hours of rest scheduled between ETTs. The primary analysis will be a paired comparison of the number of ventricular ectopic beats recorded during exercise (and recovery) at baseline and following pre-treatment with atropine. Secondary endpoints will include the presence of ventricular ectopy (yes/no), complex ventricular ectopy (couplets or greater, yes/no), and the number of runs of complex ventricular ectopy.

Prior to Enrollment	Patient recruited in clinic or by phone
	Patient will continue all outpatient medications prior to study. Specifically, beta-blocker therapy will not be stopped for this study.
Day 1	
8:00 AM	Arrive to Clinical Research Center (CRC)
	Sign consent forms
8:15 AM	Place peripheral I.V.

8:30 AM	Interrogate Device (ICD) (if ICD present)
0100741	Reprogram therapy detection zones if needed
8:45 AM	Place electrodes for ETT
0110741	
Part 1	Baseline Exercise Tolerance Test (ETT)
	Blood pressure, 12-lead ECG
8:50 AM	Start Treadmill ETT (Standard Bruce Protocol, max time=21 minutes)
	Stage 1 (1.7 mph, 10% grade, 3 mins)
8:53 AM	(if necessary) Begin Stage 2 (2.5 mph, 12% grade, 3 mins)
8:56 AM	(if necessary) Begin Stage 3 (3.4 mph, 14% grade, 3 mins)
8:59 AM	(if necessary) Begin Stage 4 (4.2 mph, 16% grade, 3 mins)
9:02 AM	(if necessary) Begin Stage 5 (5.0 mph, 18% grade, 3 mins)
9:05 AM	(if necessary) Begin Stage 6 (5.5 mph, 20% grade, 3 mins)
9:08 AM	(if necessary) Begin Stage 7 (6.0 mph, 22% grade, 3 mins)
+0:20 mins	Monitored rest recovery period
+2:00 hours	Unmonitored rest period. Patient remains on the CRC
Part 2	Atropine Pre-treatment Treadmill Exercise Tolerance Test
11:00 AM	Blood pressure, 12-lead ECG
11:05 AM	Give Atropine (0.04 mg/kg up to max of 3 mg I.V.)
	Start ETT (Standard Bruce Protocol, max time=21 minutes)
	Stage 1 (1.7 mph, 10% grade, 3 mins)
11:08 AM	(if necessary) Begin Stage 2 (2.5 mph, 12% grade, 3 mins)

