- Inability to exercise
- Marked exercise-induced hypotension (Decrease in Systolic Blood Pressure >10 mmHg despite increased workload)
- Hypertensive response (Systolic Blood Pressure >230 mmHg and/or Diastolic Blood Pressure > 115 mmHg).
- Sustained ventricular tachycardia
- Development of LBBB or intraventricular conduction delay that cannot be distinguished from ventricular tachycardia
- ST segment depression > 2 mm or ST elevation >1 mm in leads without diagnostic Q waves (except leads V1 or aVR)
- Moderate to severe angina pectoris
- Marked dyspnea or fatigue
- Ataxia, dizziness, or near syncope
- Signs of poor perfusion
- Technical difficulties in monitoring the ECG or systolic blood pressure

At the end of the exercise protocol, the recovery phase will begin. The first phase of recovery is a cooldown phase with the patient walking on the treadmill. The patient will be stopped after 2 minutes, and the patient will be asked to lay supine for the remainder of the recovery period.

Blood pressure, HR, and EKG tracings will be recorded throughout the exercise and recovery period, with patient either walking/running or laying in supine position.

Each patient will be tested individually. There will be no videotaping or audiotaping.

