10.0 Statistical Considerations

Baseline clinical characteristics will be described using frequency and percentage for dichotomous variables and median with interquartile range for continuous variables. The design of this study is a crossover trial between "no treatment" and "atropine treatment". The primary outcome variable is a continuous variable measuring the number of beats of ventricular ectopy. The null hypothesis is that no difference exists between the "no treatment" and "atropine treatment" interventions in the number of beats of ventricular ectopy. The primary analysis will use a Wilcoxon-signed ranked test. A P-value <0.05 will be used to reject the null hypothesis. A secondary outcome will be measurement of complex ventricular ectopy defined as couplets or greater. Comparisons will be made between the "no treatment" and "atropine treatment" and percentage to reject the null hypothesis. A secondary outcome will be measurement of complex ventricular ectopy defined as couplets or greater. Comparisons will be made between the "no treatment" and "atropine treatment" groups using: 1) the number of runs of complex ventricular ectopy (continuous variable) using the Wilcoxon-signed ranked test; and 2) the presence of complex ventricular ectopy (yes/no) using McNemar's test. As a pilot study, we may be underpowered to detect our primary analysis, but valuable data regarding the effect size and confidence intervals will be obtained to provide sample size estimations for subsequent larger scale clinical trials.

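### The run-count secondary ignores run length, so several couplets replaced by one sustained VT on atropine is scored as improvement, and no endpoint grades severity above the couplet

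*Combined protocol and SAP*

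**What the plan says.** Section 10.0 sets the threshold: "A secondary outcome will be measurement of complex ventricular ectopy defined as couplets or greater". It then names two comparisons between the untreated and atropine tests. One is "the number of runs of complex ventricular ectopy (continuous variable) using the Wilcoxon-signed ranked test"; the other is "the presence of complex ventricular ectopy (yes/no) using McNemar's test". The General Approach in Section 6.0 agrees, listing "complex ventricular ectopy (couplets or greater, yes/no), and the number of runs of complex ventricular ectopy"; it also has one further item, whether there was any ectopy at all.

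Run length enters only through the primary endpoint: "The primary outcome variable is a continuous variable measuring the number of beats of ventricular ectopy". There it is pooled with isolated beats, each beat having the same weight.

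"Sustained ventricular tachycardia" appears once, in the Section 6.0 list of reasons for ending exercise early. It is not an endpoint category, and its duration is not defined.

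**The concern.** The run count is meant to measure how bad the complex ectopy was, but it counts episodes whatever their length. It can fall because runs disappeared, or because several short runs gave way to one long one. These are opposite clinical results with the same score.

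The stopping criterion pushes the same way. A sustained VT adds one run and then ends the exercise in which further runs could have occurred, although recovery is still recorded.

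This matters because Section 2.0 bases the trial on preventing sudden cardiac death, and Section 7.0 names proarrhythmia as a risk of atropine. A shift from couplets to VT is the change a reader would most want to see. Section 10.0 also says that the pilot is to supply effect sizes for planning larger trials, so an ambiguous endpoint could be carried forward.

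**Working it through.** The plan gives no sample size, power or event figure for these endpoints, so there is nothing to reproduce. The check applies the plan's scoring rules to example patients.

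**Rules, from Sections 6.0 and 10.0**
- Runs = number of episodes of 2 or more consecutive ectopic beats.
- Complex ectopy = yes if runs ≥ 1.
- Beats = sum of run lengths + isolated beats.

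**Assumptions, not in the documents**
- The patient patterns below.
- A sustained VT of 75 beats (30 s at 150/min). At 120 to 200/min the same 30 s gives 60 to 100 beats.
- The 20-beat run in case C is taken as non-sustained.

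**Scores, baseline to atropine**

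| Case | Baseline | Atropine | Runs | Complex yes/no | Beats | Longest run |
|---|---|---|---|---|---|---|
| A | 1 couplet, 10 isolated | one 75-beat VT, 10 isolated | 1 to 1, tie | tie | 12 to 85, worse | 2 to 75 |
| B | 3 couplets, 10 isolated | one 75-beat VT, 10 isolated | 3 to 1, improved | tie | 16 to 85, worse | 2 to 75 |
| C | 3 couplets, 40 isolated | one 20-beat run, 5 isolated | 3 to 1, improved | tie | 46 to 25, improved | 2 to 20 |
| D | 3 couplets, 80 isolated | one 75-beat VT, 5 isolated | 3 to 1, improved | tie | 86 to 80, improved | 2 to 75 |

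For case D, baseline beats are 3 × 2 + 80 = 86 and atropine beats are 75 + 5 = 80. Presence of any ectopy is also yes in both tests in all four cases.

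**When the primary is offset.** Suppose *k* couplets are replaced by one run of *L* beats. The run-related beats rise by *L* − 2*k*, so total beats fall only if isolated beats fall by more than that. With *k* = 3:
- *L* = 75: more than 75 − 6 = 69 isolated beats must be lost.
- *L* = 60 or 100: more than 54 or 94.
- *L* = 20: more than 14.

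A long VT is therefore hard to mask in the primary, and a run of moderate length is much easier.

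**What the run-count test could conclude.** The threshold is given as "A P-value <0.05 will be used to reject the null hypothesis", with sidedness not stated; two-sided is assumed. As an extreme construction, let every patient go from two or more couplets to a single VT, with isolated beats unchanged. All run differences then favour atropine, and the exact signed-rank p-value is 2/2ⁿ:
- n = 5: 2/32 = 0.0625
- n = 6: 2/64 = 0.031
- n = 8: 2/256 = 0.0078
- n = 10: 2/1024 = 0.0020

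McNemar's test would have no discordant pairs. The beat count would point the other way with the same p-value.

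**With a grade added** (0 none, 1 isolated beats, 2 couplet, 3 non-sustained run of three or more, 4 sustained VT), cases A, B and D read 2 to 4 and case C reads 2 to 3. All four are scored as worse.

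**The case against.** The strongest reply is that the endpoints should be read together. The beat count catches cases A and B clearly. Any-ectopy and complex-ectopy yes/no together already separate none, isolated only, and complex. The reverse problem is also covered: if a 10-beat VT becomes 12 isolated beats, the primary reads 10 to 12, but runs go 1 to 0 and complex ectopy goes from yes to no. All of this stands, and a reader who inferred that the trial as a whole cannot see worsening, or that both complex-ectopy measures can report a false benefit, would be going beyond the documents. Only the run count reverses.

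A second reply is that adverse-event reporting covers dangerous worsening. Section 8.0 does include a change in the severity of an existing condition. But Section 7.0 treats ventricular arrhythmia as an expected result of the exercise, and event reporting makes no paired comparison of severity between the two tests. This is a safety channel and does not replace a graded endpoint.

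A third reply is that the pattern may be rare. Beta-blockers continue, and Section 7.0 says that participants have already completed at least two stress tests without adverse events. That is fair. The documents give no run-length or VT data, so the frequency is unknown, and the p-values above show only what the rule permits.

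**Conclusion.** The point holds for the run count. Followed as written, that endpoint scores three couplets followed by one sustained VT as 3 to 1 in favour of atropine, while the yes/no measure shows no change. The primary is a real but partial safeguard: with an assumed 75-beat VT replacing three couplets, it misleads only if more than 69 isolated beats are lost, but for a 20-beat run a loss of more than 14 is enough. No stated endpoint separates severity above the couplet.

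The reversal follows from the plan's own rules and needs no assumption beyond the pattern of runs. The beat totals rest on assumed run lengths and isolated-beat counts.

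A reader might infer that the run count should be dropped, or that a severity grade must become the leading secondary. The documents do not require either, and that choice is a matter of preference. This is a worthwhile change to the secondary endpoints of a pilot and does not invalidate the primary analysis.

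**What to change.** Keep the planned endpoints and amend the wording of Sections 6.0 and 10.0:

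- Add a worst-arrhythmia grade for each test: none; isolated beats; couplet; run of three or more beats, non-sustained; sustained VT. Compare the paired grades with the signed-rank test already named.
- Define sustained for this grade, and state how that definition relates to the undefined term in the exercise-stopping list.
- Beside the run count, report the longest run and the number of beats in runs of two or more, for each test.
- Report, by condition, the number of tests stopped for sustained VT.
- State that no claim about complex ectopy rests on the run count alone.

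The same tracings supply everything, so no new procedure is needed. There are two costs. A grade has more ties than a count, and the signed-rank test gains nothing from tied pairs, which matters in a pilot that already says it may be underpowered. There is also one more secondary analysis to report.

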11.0 Privacy/Confidentiality Issues

We describe here mechanisms in place at Vanderbilt through IRB policy to protect against such risks; these apply to all studies described below. All records are retained on password-protected computers accessible only to members of the study team. Computers containing these records are only connected to networks if they include appropriate firewalls and security measures. The identity of any individuals and their families are not to be revealed in any publication without their written informed consent.

12.0 Follow-up and Record Retention

The expected duration of this study is estimated to be 4 years. The study results will be retained for at least six years after the study is completed. At that time, the research information not already in the medical record will be destroyed.
